## **2.3 Exploratory Objectives**

- 2.3.1 To explore whether MGE administration alters 8-hydroxy-2 deoxyguanosine, peripheral blood mitochondrial function, IL-6, TNF-alpha, C-reactive protein, hepatocyte growth factor from baseline to 12 weeks compared to the placebo arm.
- 2.3.2 To explore whether MGE administration alters the microbiome from baseline to 12 weeks compared to the placebo arm.
- 2.3.3 To explore whether 8-hydroxy-2 deoxyguanosine, peripheral blood mitochondrial function, IL-6, TNF-alpha, C-reactive protein, hepatocyte growth factor and the microbiome may mediate changes in self-reported fatigue and physical function, fitness and activity from baseline to 12 weeks.
- 2.3.4 To explore whether MGE administration causes changes in cognitive speed (Digital Symbol Substitution Test) from baseline to 12 weeks compared to placebo.

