### **5.3. Exploratory outcomes**

- 5.3.1 Peripheral blood will be collected at the baseline and week 12 study visit, and will be processed to obtain serum for the measurement of cytokines including interleukin 6 (IL-6), tumor necrosis factor-alpha (TNF- $\alpha$ ), C reactive protein (CRP) and HGF and polymorphonuclear neutrophils (PMNs) to measure mitochondrial function. Cytokines and 8-OHdG will be measured using human ELISA kits (Abcam) and mitochondrial function will be assessed using a Seahorse XF Cell Mito Stress Test (Agilent).
- 5.3.2 Urine will be collected at baseline and 12 weeks to measure the oxidative stress marker 8-OHdG and urolithin A glucuronidate (UAG), a marker for the ingestion/metabolism of MGE. UAG, which is generated from the ingestion of MGE polyphenolic ellagitannins, will be measured using an LCMS-8050 triple quadrupole mass spectrometer in the Wake Forest School of Medicine Proteomics and Metabolomics Shared Resource.
- 5.3.4 Fecal specimens will be collected at baseline and at ~12 weeks using an at-home fecal sampling kit. Samples will be collected by the patient prior to the initiation of intervention and again near the completion of intervention. Patients will be asked to mail samples in a pre-paid package to the laboratory. DNA will be isolated from fecal samples using the Qiagen DNeasy PowerSoil Pro kit protocol. Metagenomic sequencing will be performed by CosmosID Inc. (Rockville, MD). In brief, DNA libraries will be prepared using the Illumina Nextera XT library preparation kit, with a modified protocol. Library quantity will be assessed with Qubit (ThermoFisher). Libraries will be sequenced on an Illumina HiSeq platform 2x150bp. Fecal samples will be read at 12M read-depth. Unassembled sequencing reads will be directly analyzed by CosmosID bioinformatics platform for multikingdom microbiome analysis and quantification of organism's relative abundance. Fecal microbiomes will be assessed by metagenomic sequencing and bioinformatics. A list of all the microbiologic species will be recorded, along with their relative abundance recorded as a % relative abundance of the total microbiome.
- 5.3.5 Digit Symbol Substitution Test (DSST) is a measure of attention and perceptual speed, amenable to change with exercise or fatigue in which participants are given a

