### **12.3 Analysis of Exploratory Objectives**

To analyze the biomarker outcomes in Objective 2.3.1, which are measured continuously, we will also use the ANCOVA approach described for the secondary objectives, and will construct 95% for the differences in the change between the two groups at 12 weeks.

To meet Objective 2.3.2, we will examine the proportion of different bacteria taxa at each time point, and will use a marginalized two-part beta regression model to account for the compositional nature of the data. If we are unable to fit this model, we will examine changes using McNemar-Bowker tests for within-person changes and for mammary and gut composition at 12 weeks.

To meet Objective 2.3.3, we will include the biomarker data in the models of the primary and secondary outcomes described above, and evaluate if the effects of the intervention on each outcome is attenuated in the presence of the biomarker. Attenuation of 10% or more in the intervention parameter estimate will indicate potential mediation in the presence of a clinically meaningful change of both the primary or secondary outcome and the biomarker of interest.

For Objective 2.3.4, we will compare the change in the DSST score between the 2 groups at 12 weeks, using a mixed model with linear contrasts.

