### **12.4 Power and Sample Size**

The minimally important difference (MID) established for the fatigue scale is 3-5, and the SD of change in our pilot study was 6.4 over 8 weeks in 12 participants. Using the upper limit of the one-sided 90% CI for this SD (9.0) to account for potential bias, indicates an effect size of  $\geq 0.33$  would be meaningful. For pilot studies, rather than calculating power based on hypothesis testing, use of 80% or 90% one-sided confidence intervals are frequently suggested. With N=30 participants per group, for a difference of 0 the upper bound of the 90% CI is 0.33; i.e., if we observe no difference between the groups, it would be unlikely that the true effect size is greater than 0.33. To adjust for 5% drop out we will inflate our sample to 32/group. For secondary objectives, which are based on baseline and follow-up measures, we will estimate 90% confidence intervals for the differences between the two groups for the secondary measures of interest. Adherence rates will be estimated using pill counts and examined using a mean and 95% confidence interval. Subgroup analyses of the outcomes will be explored among those that achieved  $\geq 80\%$  adherence vs. those that did not.

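### The 10% attenuation rule for mediation carries no interval and no biomarker threshold, so a biomarker that responds to MGE but has no link to fatigue can be labelled a potential mediator

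*Combined protocol and SAP*

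**What the plan says.** Objective 2.3.3 (section 2.3) asks whether six named biomarkers and the microbiome mediate the effects of MGE; its list ends "hepatocyte growth factor and the microbiome may mediate changes in self-reported fatigue and physical function, fitness and activity". For the analysis, section 12.3 states "we will include the biomarker data in the models of the primary and secondary outcomes described above" and compares the intervention estimate with and without the biomarker. The decision rule is "Attenuation of 10% or more in the intervention parameter estimate will indicate potential mediation in the presence of a clinically meaningful change", and the condition reads in full "in the presence of a clinically meaningful change of both the primary or secondary outcome and the biomarker of interest".

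Section 12.3 also plans an interval for each continuous biomarker: "will construct 95% for the differences in the change between the two groups at 12 weeks" (read here as a 95% confidence interval). That interval concerns the effect of MGE on the biomarker. The plan gives one size for a meaningful difference, in section 12.4: "The minimally important difference (MID) established for the fatigue scale is 3-5". It gives none for any biomarker, and it does not say whether the meaningful change is within or between arms. On timing, section 5.3 says "Peripheral blood will be collected at the baseline and week 12 study visit".

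**The concern.** Mediation needs two links: MGE must move the biomarker, and the biomarker must be related to the outcome. The attenuation is built from both, but the rule looks only at its point estimate. The condition on biomarker change and the planned biomarker interval both address the first link. Neither addresses the second.

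For a biomarker that MGE shifts but that is unrelated to fatigue, the true attenuation is zero. The estimated attenuation is then the sampling error of the biomarker slope multiplied by a real shift, so a larger shift means more noise. Requiring a meaningful biomarker change therefore does not remove such cases, and the planned biomarker interval will tend to look like support. With no biomarker threshold stated, the condition also cannot be applied in a reproducible way. At stake is the mechanistic reading of the pilot: a biomarker that merely responds to MGE could be reported as a potential mediator of fatigue.

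**Working it through.** **Inputs from the plan (section 12.4).** "the SD of change in our pilot study was 6.4 over 8 weeks in 12 participants"; planning SD 9.0; 30 analysed per arm; smallest meaningful fatigue difference 3 points.

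**The plan's own figures reproduce.** Upper one-sided 90% limit for the SD: 6.4 × √(11/χ²(0.10; 11 df)) = 8.99, stated as 9.0. Bound at a zero difference: z(0.90) × √(2/30) = 0.331, stated as 0.33. Effect size: 3/9.0 = 0.33. The plan states no error rate for the 10% rule.

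**Assumed, not in the documents.** MGE shifts the biomarker by 0.5 SD. The biomarker condition is an absolute between-arm difference of at least 0.33 or 0.5 SD. The fatigue condition is an observed between-arm benefit of at least 3 points. The data are normal and analysed as change scores.

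**Formula.** With a the arm difference in the biomarker, b the biomarker-to-fatigue slope and c the total effect, (c − c adjusted)/c = a × b / c.

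**Hand check, SD 9.0, no link.** The standard error of b is about 9.0/√58 = 1.18 points per biomarker SD. With a = 0.5, the noise in a × b is 0.5 × 1.18 = 0.59 points. Ten per cent of a 3-point effect is 0.3 points, which is 0.3/0.59 = 0.51 standard errors. The cut-off lies well inside the noise.

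**Simulation of the rule: biomarker shifted 0.5 SD, no link to fatigue (100,000 trials per row).** Each pair is for a condition of 0.33 SD / 0.5 SD.

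| SD of change | True benefit | Trials with observed benefit ≥3 | Flagged, among those | Flagged, among all trials |
|---|---|---|---|---|
| 9.0 | 3 | 50% | 18.2 / 13.8% | 9.1 / 6.9% |
| 9.0 | 5 | 81% | 15.6 / 12.2% | 12.6 / 9.8% |
| 6.4 | 3 | 50% | 14.4 / 11.4% | 7.2 / 5.7% |
| 6.4 | 5 | 89% | 11.4 / 9.4% | 10.1 / 8.3% |

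The last column is the product of the two before it, for example 0.50 × 18.2% = 9.1%. The bottom row uses 0.888 before rounding.

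Among trials with the observed benefit (SD 9.0, true benefit 3) and before any biomarker condition, the 5th to 95th percentiles of attenuation are −25% to +25%, although the true value is zero.

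**What the two intervals show in these flagged trials.** The planned 95% interval for the biomarker's arm difference excludes zero in about 73–81% (0.33 SD) or 94–95% (0.5 SD) of them, so it appears to confirm the flag. The 95% interval for the biomarker-to-fatigue coefficient includes zero in 84–91% of them, so it would expose most.

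**Biomarker that MGE does not affect** (assumed correlation with fatigue 0.3–0.5, among trials with the observed benefit). Flagged in about 8–17% at 0.33 SD and about 3–5% at 0.5 SD.

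**Sensitivity to the model.** With baseline-adjusted models (SD of change 9.0, assumed baseline correlation 0.5–0.7, raw-SD thresholds), the shifted, unlinked biomarker is flagged in 17–25% or 12–17%, and the unaffected one in 4–13% or 0.3–3%.

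**Bootstrap interval for the indirect effect** (change-score model, 3,000 trials × 1,000 resamples). For the shifted, unlinked biomarker, the 95% percentile interval excludes zero in 2.1–2.4% of all trials and in 6–9% of flagged trials.

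**The case against.** The best defence is that the plan already limits both the claim and the rule. The objective is exploratory, and the label is potential mediation. The cut-off works only together with a meaningful change in outcome and biomarker. If the biomarker condition is as strict as 0.5 SD, it largely handles biomarkers that MGE does not affect. All of this stands, and it keeps the point minor.

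Three stronger readings are tempting, and the documents do not support them:

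- A reader might infer that no planned analysis estimates the link from biomarker to fatigue. The model with the biomarker added yields that coefficient and its standard error. What is missing is any commitment to report it or use it in the rule.
- A reader might infer that 10% attenuation by itself declares mediation. Section 12.3 attaches two further conditions. The flag rates found with the biomarker condition removed (20–48% for an unaffected biomarker at SD 9.0 and correlation 0.3–0.5) therefore do not describe this plan.
- A reader might multiply across six biomarkers, which gives at least one flag in 51–86% of trials with an observed benefit. That calculation applies no biomarker condition and assumes that all six are shifted by 0.5–0.8 SD, all unlinked to fatigue and independent of each other. Nothing in the documents supports that.

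It is also fair to object that the simulation uses change scores, whereas section 12.1 plans a constrained mixed model over all visits, and that the shifts and thresholds are assumed. The rates are therefore indicative. The missing interval and missing biomarker threshold depend on none of these assumptions.

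**Conclusion.** The concern holds, at minor severity. As written, the rule can call a biomarker a potential mediator when MGE shifts it but it has no link to fatigue. Under the stated assumptions (30 per arm, SD 6.4–9.0, true benefit 3–5 points, 0.5 SD shift), this occurs in about 11–18% or 9–14% of trials with an observed benefit of at least 3 points. Across all trials it is about 7–13% or 6–10%. The planned biomarker interval does not reveal these cases. An unaffected biomarker is a problem mainly if the unstated threshold is nearer 0.33 SD than 0.5 SD. The primary analysis and the sample size are not affected.

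**What to change.** In section 12.3, for each continuous biomarker, report beside the attenuation:

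- the indirect effect (arm-to-biomarker coefficient times biomarker-to-outcome coefficient, adjusted for baseline biomarker and baseline outcome) with a 95% percentile bootstrap interval;
- the biomarker-to-outcome coefficient with its 95% interval;
- the already planned interval for the biomarker's arm difference.

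For fatigue, fit this at week 12, because blood is drawn only at baseline and week 12. Use the same participants with and without the biomarker. Describe potential mediation from these estimates and intervals rather than from the 10% point-estimate rule. If the meaningful-change condition is kept, state it in advance for each biomarker as a between-arm difference.

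The cost is a few sentences and short bootstrap code, with no new data. The intervals will be wide (median 95% width about 3–5 fatigue points at correlations of 0.3–0.5) and will support fewer mediation statements. For a true mediator (0.5 SD shift, correlation 0.3–0.5), the interval excluded zero in only 29–51% of simulated trials, or 38–56% with baseline adjustment. The present rule flags 50–88% of such trials that show a benefit. The interval should therefore be reported as an estimate of uncertainty and not turned into a pass/fail test.

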### **12.4 Power and Sample Size**

The minimally important difference (MID) established for the fatigue scale is 3-5, and the SD of change in our pilot study was 6.4 over 8 weeks in 12 participants. Using the upper limit of the one-sided 90% CI for this SD (9.0) to account for potential bias, indicates an effect size of  $\geq 0.33$  would be meaningful. For pilot studies, rather than calculating power based on hypothesis testing, use of 80% or 90% one-sided confidence intervals are frequently suggested. With N=30 participants per group, for a difference of 0 the upper bound of the 90% CI is 0.33; i.e., if we observe no difference between the groups, it would be unlikely that the true effect size is greater than 0.33. To adjust for 5% drop out we will inflate our sample to 32/group. For secondary objectives, which are based on baseline and follow-up measures, we will estimate 90% confidence intervals for the differences between the two groups for the secondary measures of interest. Adherence rates will be estimated using pill counts and examined using a mean and 95% confidence interval. Subgroup analyses of the outcomes will be explored among those that achieved  $\geq 80\%$  adherence vs. those that did not.

### **12.5 Estimated Accrual Rate**

The expected accrual is 64 participants. We anticipate accruing an average of 3 participants per week.

### **12.6 Estimated Study Length**

Participants will be followed for a total of 12 weeks for study procedures. A 30-day phone visit will be conducted after the last dose of the study drug thus the study will be completed 12-16 weeks after the last participant is accrued.

Pilot study of muscadine grape extract to improve fatigue among older adult cancer survivors (FOCUS)

Wake Forest Baptist Comprehensive Cancer Center

WFBCCC #98320

## Appendix L - Frailty Index Calculation Form

**Score will be programmed to calculate automatically, after other forms are entered into the database.**

**Study team to review weight loss collected on baseline form:**

1. Have you had more than 10 pounds of unintentional weight loss in the past year? (Baseline form)  
Yes  No

**Study team to record the following:**

2. Review the response to question #7 on the CES-D survey which states "everything I did was an effort". Did the participant answer either "3-4 days /week" or "5-7 days per week"? Yes  No
3. Review the response to question #20 on the CES-D survey which states "I could not get going". Did the participant answer either "3-4 days /week" or "5-7 days per week"? Yes  No

**Study team to review data from 4-meter walk trials from SPPB are recorded**

4-meter walk test, faster of 2 trials (seconds, with up to 2 decimal places)

**Study team to review data from grip strength testing are recorded:**

Strongest trial for right hand: (kg)

Strongest trial for left hand: (kg)

**Study team to review MLTQ was collected and recorded.**

## Appendix R: Digit Symbol Substitution Test (DSST) Script

\*\*\*This is a sample of the test. Permission was received to obtain and use the full test.\*\*\*

Digits Symbol Substitution Test																								
1	2	3	4	5	6	7	8	9																
↔	↓	≡		≠	□	◊	€	ℳ																
2	9	2	9	4	9	4	9	1	8	9	3	1	7	2	3	6	4	8	3	1	7	8	2	5
4	7	1	7	5	8	4	1	5	2	6	9	9	5	6	7	6	2	9	4	8	7	2	8	6
8	6	2	8	2	9	4	7	4	8	6	7	3	1	6	2	1	8	7	4	3	1	6	2	9
2	5	4	6	1	6	3	1	2	7	2	6	4	9	1	8	5	7	1	5	4	5	3	9	2
3	9	7	1	7	1	3	5	7	6	1	6	5	9	1	3	1	3	9	8	9	7	3	4	3

Next I am going to have you copy some symbols. Take a look at these boxes up top. Notice that they have a number up top and a symbol below. Each number has its own symbol.

Now look at the boxes down here. The boxes have numbers in the top but the bottom is empty. What I am going to have you do is put the symbol in bottom boxes that should go there. Let me demonstrate.

Here is the 6, the 6 has this symbol, so you would put in the box under the 6. Here is the 8, the 8 has this symbol, so you would put in the box under the 8. Here is the 3, the 3 has this symbol, so you would put in the box under the 3.

Now I am going to have you fill in the boxes up to the heavy black line here.

Good! Now that you know how to do them, when I say BEGIN, I am going to have you start here and fill in as many boxes as you can without skipping any. Work as quickly as you can without making any mistakes. Complete each row before going to the next. Keeping working until I tell you to stop.

Ready? BEGIN.
